5.1.1. Sample Size. We plan to enroll 88 fully-ambulatory persons with MS (i.e., 44 per condition) who have objective impairment in CPS; this is based on a power analysis and presumed 25% attrition. Of the 88 total participants, 65 will be recruited at Kessler Foundation, as this study is currently ongoing and was partially completed at the University of Alabama at Birmingham. The minimal sample size of 66 persons with MS (i.e., 33 per condition) was determined based on power analysis using previous effect sizes from our preliminary RCT of TMWX training on CPS outcomes (i.e., $\eta_p^2=0.11$) and standard assumptions of Type I error (0.05) and power (0.80) based on analysis of covariance (ANCOVA) on follow-up SDMT scores, controlling for baseline SDMT score [19]. We note that this rate of attrition exceeds that of the overall average of exercise training studies among persons with MS based on a systematic review [28] making our calculations conservative.

5.1.2. Recruitment. Prospective participants will be recruited directly through the community, local chapter of the National MS Society (NMSS), and our laboratory database of previous participants with MS who have inquired about participating in future studies. Advertisements for the study will be distributed through local MS centers, facilitators of local MS support groups, *MS Connection* publications, and e-mail distributions. As a backup plan, we may recruit prospective participants with MS through the North American Research Committee on Multiple Sclerosis (NARCOMS) patient registry or iConquerMS if enrollment is slow.

5.1.3. Screening. The screening process for potential participants will first involve a phone screen, followed by an in-person screen. Via telephone, the project coordinator will obtain the following information from potential participants:

- Age between 18-59 years
- Definite diagnosis of MS
- Relapse-free for 30 days, not acutely taking corticosteroids
- No major depressive disorder, schizophrenia, bipolar disorder I or II, substance abuse disorder
- Not currently taking medications that can affect cognition (i.e., benzodiazepines, anti-psychotics)
- Not having known/diagnosed cardiovascular, metabolic, or kidney disease
 - If the prospective participant does report having known/diagnosed cardiovascular, metabolic or kidney disease, then physician's approval will be required in order to be eligible for study enrollment.

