- Confirmation of on at least 6-months of a stable disease-modifying therapy (DMT) regimen
- Right-handedness
- Not engaging in at least 150 minutes of moderate-to-vigorous physical activity behavior
- Not currently engaging in cognitive rehabilitation or participating in regular brain fitness activities
- Not currently pregnant

If a participant passes the above inclusion/exclusion criteria, the project coordinator will then administer the TICS-M over the phone to ensure that all participants are not decisionally impaired. In order to pass this inclusion criterion, participants must demonstrate TICS-M scores of 18 or higher. We further will administer the Mini Mental State Examination (MMSE) during the in-person screen to confirm a lack of decisional-impairment (see 5.2 Research Procedures below). If participants are not decisionally impaired, the project coordinator will request contact information for the potential participant's neurologist, whereby they will email or fax a letter asking them to verify a definite MS diagnosis and confirmation that the participant has been on a stable DMT regimen for at least 6-months. Upon receipt of these materials from the participant's neurologist, we will perform an in-person screening visit after informed consent is provided (See 5.2 Research Procedures below). If a participant does not qualify for the study, they will be notified via telephone and asked if they would be willing to be contacted for future research opportunities from our laboratory.

5.1.4 Randomization. As this study represents a RCT, participants will be randomly assigned to either a treadmill walking exercise or active control condition. We anticipate that 44 participants will be randomly assigned to each condition. Briefly, the treadmill walking exercise condition will involve supervised treadmill walking exercise that progresses in terms of duration and intensity over the course of 3-months. Participants will attend 36 sessions that will each last approximately 60 minutes, and will take place 3-times per week. The active control condition will involve supervised stretching-and-toning activities that will occur over the course of 3-months. Participants will attend 36 sessions that will each last approximately 60 minutes, and will take place 3-times per week.

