5.2 Research Procedures

5.2.1 Outcomes.

Cognition: This study will involve several neuropsychological tests of cognitive functioning. Based on our pilot work, the primary neuropsychological outcome for measuring cognitive processing speed (CPS) in the current proposal will be the oral version of the Symbol Digit Modalities Test (SDMT) [35]. This test is considered a more pure measure of CPS, as it relies less on working memory (i.e., the central executive) than other neuropsychological measures that are commonly used in MS research (i.e., the Paced Auditory Serial Addition Test; PASAT) [36]. The SDMT further is a better predictor of whole-brain atrophy and T2-lesion volume than the PASAT [36]. Indeed, the SDMT has emerged as the best predictor of future cognitive decline in persons with relapsing-remitting MS [37]. As such, it is often considered to be a proxy of generalized cognitive

impairment in this population [38]. The current proposal further will include other exploratory neuropsychological measures of CPS. Those measures include the PASAT [39], modified flanker task [40], Pattern Comparison Test [41], and DKEFS Trail-Making and Color-Word Interference Tests [42]. Such measures will be included to examine the generalizability of the effects of treadmill walking exercise training on the overall construct of CPS. Those tests have strong psychometric properties (e.g., [43]), and are commonly-used to document the efficacy of cognitive rehabilitation interventions in persons with MS (e.g., [44]).

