The primary analysis will involve a statistically efficient, hierarchical step-down testing approach using ANCOVA models to examine differences in post-test outcomes of CPS and thalamocortical RSFC (i.e., examining group differences in follow-up outcomes, adjusting for baseline as covariate). The hierarchical step-down approach presents a series of conditional hypothesis tests after the primary hypothesis is assessed. This *a priori* specifies the importance and order of the testing so that each hypothesis is tested in order, until the first non-significant result occurs. Once a null-hypothesis is not rejected, all formal testing will stop, and all subsequent results will be reported as *post-hoc* and/or descriptive. This protects against Type I error as it assumes that the outcomes are correlated, and the overall *p*-value is protected by reporting the largest *p*-value for all the tests. As the primary study outcome involves CPS based on SDMT scores, we will first perform an ANCOVA model on follow-up SDMT score, with group (intervention or control) as a between-subjects factor and baseline SDMT score as the covariate. If statistically significant (i.e., *p*<.05), we will then assess the effects of the intervention on the general construct of CPS using MANCOVA and on the individual CPS tests using separate, univariate ANCOVA models.

Regarding thalamocortical RSFC, the next set of analyses will involve performing ANCOVA models on follow-up RSFC between the thalamus and frontal cortical areas (e.g., SFG, MFG [21]), respectively, with group (intervention or control) as a between-subjects factor and baseline RSFC between the thalamus and frontal cortical areas, as the covariates. We will require an alpha of .05 (corrected for multiple comparisons) for significance for thalamocortical RSFC outcomes. The correction for multiple comparisons will be achieved by establishing a suitable voxel cluster-level threshold through Monte Carlo simulations (using the 3dClustSim program, part of the AFNI suite of image analysis programs). Based on our pilot work [19,21], we expect significant group differences in SDMT score and RSFC between the thalamus and frontal cortical areas, respectively, at follow-up after controlling for baseline scores, whereby participants who are randomly assigned to the intervention group will demonstrate greater SDMT scores and stronger thalamocortical RSFC at follow-up compared with those who are randomly assigned to the control group.

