Sample Size Considerations. As described in the original application (i.e., R01HD091155-A1), we conducted a conventional power analysis using G*Power (Version 3.1.9.5) and estimated the appropriate sample size for detecting differences in follow-up SDMT scores, controlling for baseline score (Specific Aim 1). Using G*Power, this was accomplished using the 'F test' selection within the 'Test' family menu, and the Statistical Test of 'ANCOVA: Fixed effects, main effects and interactions'. The effect size ($\eta_p^2=0.11$) for the power analysis was computed from our pilot RCT¹² of TMWX training compared with a waitlist control condition on SDMT scores in persons with MS who had mild ambulatory disability, but not CPS impairment. That effect size was smaller than the effect sizes for thalamocortical RSFC outcomes, and thus was included in the main power analysis as a conservative approach. The power analysis included standard assumptions of alpha (0.05) and beta (0.80). The power analysis indicated that the minimal total sample size for testing group differences on follow-up SDMT scores, controlling for baseline scores should be 66 participants (33 per group). This supports our goal of recruiting 88 participants (44 per condition) as yielding adequate power, based on retention of 75% of the enrolled participants. The current application proposes a change of grantee organization whereby the final 72 participants will be enrolled at KF. We will explore the possible influence of study site on the outcomes in *post-hoc* sensitivity analyses. We expect that the effects of study site are likely negligible given the constants of the study team and standardized manuals of operating procedures that guide all study aspects.

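### The step-down in protocol section 5.3 claims Type I error protection, but its second step tests five or six individual CPS measures with no order and no alpha adjustment, and it conflicts with the SAP sequence

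*Combined protocol and SAP*

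**What the plan says.** Protocol section 5.3 (Analysis) presents the primary analysis as a hierarchical step-down in which "each hypothesis is tested in order, until the first non-significant result occurs". After a failure, formal testing ends and later results become post hoc or descriptive. The section says that this protects against Type I error because the outcomes are assumed to be correlated, and that the overall p-value "is protected by reporting the largest" p-value over all the tests.

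The steps in section 5.3 are:

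1. ANCOVA on follow-up SDMT at p<.05.
2. If significant, a MANCOVA on the general CPS construct and tests "on the individual CPS tests using separate, univariate ANCOVA models".
3. As the next set of analyses, ANCOVAs on RSFC, with a voxel-cluster correction.

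Three other places bear on step 2:

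- Protocol section 5.2.1 (Cognition) introduces the further CPS tests thus: "The current proposal further will include other exploratory neuropsychological measures of CPS". It names five: PASAT, flanker, Pattern Comparison, Trail-Making and Color-Word Interference. Section 5.2.3.2 pairs Letter Comparison with Pattern Comparison, which could make six.
- The SAP (Statistical Design and Power), Specific Aim 1, goes from the SDMT straight to RSFC, with no CPS tests between.
- The SAP, under Exploratory Aim 3, treats cognitive outcomes beyond the SDMT as exploratory.

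**The concern.** A fixed sequence controls the familywise error because hypotheses are tested one at a time in a stated order. Step 2 instead tests several hypotheses side by side, each at 0.05. The only multiplicity correction in section 5.3 is the voxel-cluster threshold for RSFC, so the claimed protection does not extend to the individual CPS tests. Section 5.3 labels the univariate models for the functional outcomes exploratory and descriptive, but gives the CPS models no such label.

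Two things are at stake. Individual CPS results are meant to show that an SDMT effect generalises, and they could be presented as formally significant at more than the stated error rate. Also, RSFC is named a primary outcome in the protocol abstract and in the SAP, yet in section 5.3 it stands behind tests that section 5.2.1 calls exploratory.

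The justification is also wrong. A fixed sequence controls error under any correlation, and its adjusted p-value at a step is the largest p-value up to and including that step, not the largest over all the tests.

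**Working it through.** **Inputs from the documents.** Partial eta-squared 0.11 and "standard assumptions of Type I error (0.05) and power (0.80") (protocol 5.1.1); G*Power test "ANCOVA: Fixed effects, main effects and interactions" (SAP, Sample Size Considerations); 66 analysed and 88 enrolled, 1:1. **Assumed, because the documents give no figure:** equal correlations of 0.3, 0.5 or 0.7 among the CPS tests and with the SDMT, and the effects on the other CPS tests.

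**The plan's own figure.** f² = 0.11/0.89 = 0.1236. With N = 66, λ = 0.1236 × 66 = 8.16 on 1 and 63 df, and power at 0.05 is 0.803. Then 66/0.75 = 88. Both figures reproduce. For two equal groups the standardised difference is 2 × √0.1236 = 0.70 SD.

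**SDMT.** It is tested first, alone, at 0.05, so its error rate is 5%. If the SDMT null is true, nothing later is tested in more than 5% of trials.

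**Individual CPS tests, reference values.** Once testing reaches them, k independent null tests at 0.05 give 1 − 0.95^k: 22.6% for five and 26.5% for six.

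**With the plan's own preconditions.** Simulated chance per trial of at least one false CPS claim, SDMT at 80% power (five / six tests):

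| Assumed correlation | SDMT must be significant; no CPS test affected | SDMT and MANCOVA must be significant; no CPS test affected | SDMT and MANCOVA must be significant; one CPS test affected at 80% power |
|---|---|---|---|
| 0.3 | 16% / 18.5% | 3.5% / 3.5% | 11.9% / 13.9% |
| 0.5 | 12.7% / 14.5% | 2.8% / 2.8% | 10.4% / 12.0% |
| 0.7 | 8.9% / 10.0% | 2.0% / 2.0% | 7.6% / 8.8% |

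Simulation with 33 per arm and a true effect of 0.7 to 1.0 SD on one CPS test extends the last column to 8-13% (five tests) and 9-16% (six). The MANCOVA protects while every CPS null is true. Once one test has a real effect, the MANCOVA tends to be significant for that reason and the remaining nulls are tested unprotected.

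**Blocking of RSFC.** Suppose the SDMT and all five further CPS tests each have 80% power. Given a significant SDMT, at least one of the five fails in 51%, 40% and 29% of trials at correlations 0.3, 0.5 and 0.7. On a strict reading, each such failure ends formal testing before RSFC. Under the SAP sequence it does not.

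**Largest-p wording.** For ordered p-values .01, .03, .04, .20, the fixed-sequence adjusted values are the running maxima: .01, .03, .04, .20. The SDMT keeps .01. A single overall value would be .20.

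**The case against.** The strongest reply is that these tests are exploratory already. Section 5.2.1 says so, the SAP leaves them out of the chain, and only the SDMT and RSFC are named primary. That is fair as to probable intent. It does not settle what section 5.3 says, which puts the tests inside the formal chain without that label, so the passages must be reconciled.

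A second reply is that the general stopping rule implies that the MANCOVA must be significant first. It does imply this, although the text never says so, and where no CPS test is affected the error is then controlled. The inflated case needs one CPS test with an effect at or above the planning effect while the other, correlated speed tests have none. That configuration is specific, but a procedure said to protect against Type I error should cover it.

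Two stronger readings are tempting, and the documents do not support them.

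- A reader might infer that the largest-p rule overrides a significant SDMT. Section 5.3 judges the SDMT first, on its own p<.05, and demotes only results after a failure. The sentence is also compatible with ordinary running-maximum adjusted p-values. It is ambiguous, but it contains no override rule.
- A reader might infer that the CPS error rate is three to four times the stated 5%. That holds only in part of the range, chiefly for tests already reached or with no precondition at all. Per trial, with the SDMT precondition counted, the range is about two to four times (9-19%), and it falls below 5% if the MANCOVA is also required and no CPS test is affected.

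**Conclusion.** The concern holds for the individual CPS tests and for the order of testing, not for the SDMT. The claimed Type I error protection does not cover the five or six CPS ANCOVAs. The chance per trial of at least one false claim among them is:

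- about 9-19% if only the SDMT must be significant;
- 2-4% if the MANCOVA must be too and no CPS test is affected;
- about 8-16% with both preconditions and one test truly affected by 0.7-1.0 SD.

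These figures rest on assumed equal correlations of 0.3-0.7, assumed CPS effects, 33 per arm and the SDMT at its planning effect. The upper ends belong to six tests, which requires Letter Comparison to be scored separately.

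The conflict between section 5.3 and both section 5.2.1 and the SAP rests on the text alone. Its most serious consequence is that a failed exploratory test could end formal testing of a primary outcome. The justification sentence is wrong in its reasoning and could be misread as replacing the SDMT p-value with a single overall one.

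**What to change.** In section 5.3, take the CPS MANCOVA and the individual CPS ANCOVAs out of the formal chain and label them exploratory, so that the sequence is SDMT then RSFC, as under Specific Aim 1 of the SAP. If formal claims on individual CPS tests are wanted, place them after RSFC with Holm across them, which holds the error within that family at 5% or less. In that case, also state which RSFC result opens the CPS step, since the SAP tests two regions.

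Replace the sentence on correlated outcomes and the largest p-value with: *the adjusted p-value at each step is the largest of the p-values up to and including that step; SDMT keeps its own p-value.*

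The cost is a few sentences and fewer formal claims on individual CPS tests. The SDMT stays at 0.05, so 66 analysed and 88 enrolled are unchanged.

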5.2.7 Follow-up Testing. Within 48 hours following the completion of the last treadmill walking exercise training/stretching-and-toning session, the Project Coordinator will contact the participant and schedule them for follow-up testing. As is the case for baseline, this will occur across 2 visits that will be separated by a 2-day period. The first Follow-Up Visit will occur at the Kessler Foundation, and the second Follow-Up Visit will occur at the Rocco Ortenzio Neuroimaging Center at Kessler Foundation. Procedures for Follow-Up Visits 1 and 2 will be identical to that of Baseline Visits 1 and 2. Participants will be remunerated \$100 at the conclusion of Follow-Up Visit 2 in the form of a gift card.

5.3 Analysis. The data analyses will be overseen by a biostatistician (i.e., [name] at Pythagoras, LLC) and follow intent-to-treat principles (i.e., include all persons once randomized regardless of adherence and/or compliance). In the case of a drop-out, missing data will be imputed by carrying the last observed value forward. We further will perform exploratory data analyses in only those who completed follow-up testing (i.e., completer's or per protocol analysis) and in those who demonstrated good adherence (i.e., attended at least 83% of sessions) and compliance [69]. The analytic plan will account for several potential confounders of the effects of progressive TMWX training on the outcome measures; these confounders include MS duration, BMI, age, sex, T₂-lesion volume, and relapse rate, if those variables differ between groups. Further, all study data are entered and analyzed in SPSS version 25 (IBM Inc., Armonk, NY).

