Effect sizes will primarily be expressed as partial eta-squared (η_p^2) [70]. Effect sizes further will be reported as Cohen's d in order to characterize the standardized mean difference of the effects of TMWX training on the outcomes [70] and for ease of inclusion in subsequent meta-analyses [70]. The effect sizes from the interaction terms from the ANCOVAs on CPS, thalamocortical RSFC, functional outcomes, and CRF will serve as effect sizes for the subsequent power analyses required for informing the development of a multi-site, Phase II/III RCT.

6. Work Schedule

Objective	Year 1		Year 2				Year 3				Year 4			
	Quarter 3	Quarter 4	Quarter 1	Quarter 2	Quarter 3	Quarter 4	Quarter 1	Quarter 2	Quarter 3	Quarter 4	Quarter 1	Quarter 2	Quarter 3	Quarter 4
Hire personnel	x	x												
Train personnel		x												
Purchase equipment and supplies	x													
IRB Approval	x													
Recruit participants		x	x	x	x	x	x	x	x	x	x			
Data collection and entry		x	x	x	x	x	x	x	x	x	x			
Data analysis										x	x			
Present data at scientific meetings									x	x	x	x		
Manuscript preparation and publication								x	x	x	x			

7. Cost analysis

See attached budget.

References

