improvement at the brain-systems level in the general population²⁸. As pre-conditions of the mediation analysis, we will first perform correlations among group (i.e., exercise or control), change in SDMT scores, and change in RSFC between the thalamus and right MFG and ACC, respectively, using Spearman's rho rank-order correlations (ρ)⁹¹ to test if those outcomes are interrelated. Consistent with our pilot work¹², we expect that TMWX training will be associated with improvements in CPS and increases in thalamocortical RSFC. Moreover, we expect that improvements in CPS will be associated with increases in thalamocortical RSFC. Then, to establish mediation, we will perform hierarchical linear regression models for evaluating each of the two mediators (i.e., changes in RSFC between thalamus/right MFG, and RSFC between thalamus/ACC, respectively), separately. This will involve regressing change in SDMT score on group in Step 1 and then adding change in the mediator in Step 2. In order to establish mediation, if the pre-conditions are met, group must influence change in SDMT in Step 1, and the mediator must influence change in SDMT score in Step 2 of the regression as well as attenuate the effect of group on SDMT scores (i.e., the effect of group on SDMT should be reduced and become non-significant between Step 1 and Step 2)⁸⁹. As such, we expect significant effects of group on change in CPS, and that the effect of group (i.e., exercise or control) on change in CPS will be attenuated, but not reach zero, when accounting for the effects of changes in thalamocortical RSFC. In other words, we expect that changes in thalamocortical RSFC will be partial mediators of the effects of TMWX training on CPS in persons with MS with impaired CPS.

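### The RSFC outcome has no defined per-participant value, and the only stated correction, a voxel cluster threshold, cannot act on the planned region-by-region ANCOVAs

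*Combined protocol and SAP*

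**What the plan says.** Section 5.3 of the protocol plans ANCOVAs on follow-up RSFC between the thalamus and frontal areas, adjusted for baseline RSFC, with an open list of example regions. Specific Aim 1 in the statistical part names two regions, right MFG and ACC, with a separate ANCOVA for each, run only if the SDMT test is significant. Both places require a corrected alpha of .05 for RSFC and give the same single method: "The correction for multiple comparisons will be achieved by establishing a suitable voxel cluster-level threshold through Monte Carlo simulations", using 3dClustSim in AFNI.

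Three other statements treat RSFC as an ordinary per-person variable:

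- Section 5.3 reports partial eta-squared and Cohen's d, and carries RSFC forward to the planning of a later trial: "The effect sizes from the interaction terms from the ANCOVAs on CPS, thalamocortical RSFC, functional outcomes, and CRF will serve as effect sizes".
- Specific Aim 2 uses change in RSFC for each region as a regressor: "This will involve regressing change in SDMT score on group in Step 1 and then adding change in the mediator in Step 2". It also correlates that change with group and with SDMT change.
- Section 5.3 says that "all study data are entered and analyzed in SPSS version 25".

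Section 5.2.1 says that the scan measures connectivity between thalamus and frontal cortex. It gives no mask, averaging rule, transformation or extraction rule.

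**The concern.** A cluster-extent threshold controls error over a map of many voxelwise tests. It has no role in a model with one outcome value per participant. The plan therefore describes two different analyses of RSFC under one name and does not say how the map becomes the number.

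This matters because RSFC is named as a primary outcome alongside SDMT, is the only proposed mechanism in Aim 2, and is listed as a source of effect sizes for the next trial. Depending on how the gap is filled, either the promised correction across regions is absent, or the reported effect size is conditioned on having passed a threshold for the arm difference. The team could make that choice after seeing the maps.

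**Working it through.** **The plan's own figure.** The only design calculation is for SDMT, using G*Power's "ANCOVA: Fixed effects, main effects and interactions". Inputs from Sample Size Considerations: partial eta-squared 0.11, alpha 0.05, power 0.80, two groups, one covariate.

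- f² = 0.11/0.89 = 0.124; noncentrality = f² × N; degrees of freedom 1 and N − 3.
- Power is 0.797 at N = 65 and 0.803 at N = 66, so 66 reproduces. 66/0.75 = 88 also reproduces.

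The sample size is not in question. The figure of 66 is used below as the number analysed.

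**If RSFC is a region mean.** Each region gives one test and there is no voxel search, so 3dClustSim has nothing to act on. For two independent tests at .05, the chance of at least one false finding is 1 − 0.95² = 0.0975. With correlated test statistics (bivariate normal, two-sided):

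| Between-region correlation | Family-wise error |
|---|---|
| 0 | 0.098 |
| 0.5 | 0.091 |
| 0.7 | 0.083 |
| 0.9 | 0.070 |

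The correlation is an assumption; the documents give none. These figures apply once SDMT has been declared significant, and if the two regions are not tested in a fixed order.

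**If RSFC is averaged over surviving clusters.** With 66 analysed there are 63 error degrees of freedom. A voxel enters a cluster only if |t| exceeds the cluster-forming value, so its partial eta-squared is at least t²/(t² + 63). The plan does not state that threshold, so three are shown:

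| Assumed voxel p | t (63 df) | Smallest partial eta-squared |
|---|---|---|
| .01 | 2.656 | 7.054/70.054 = 0.101 |
| .005 | 2.909 | 8.462/71.462 = 0.118 |
| .001 | 3.452 | 11.916/74.916 = 0.159 |

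At N = 88 (85 df) the floors are 0.076, 0.089 and 0.120. With no effect and no selection, the expected value at 63 df is 1/(1 + 63) = 0.016.

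A simulation separates selection from a real focal effect by applying the same mask to fresh data. It assumed 33 per arm, a region of 12×12×12 voxels, smoothness of 3 voxels, voxel p .001, a 5% extent threshold and shared between-voxel variance of 0.3 to 0.5. It used a two-sample test without the baseline covariate and kept clusters favouring exercise.

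| True voxel d | Partial eta-squared, same data | Same mask, fresh data |
|---|---|---|
| 0 | 0.24-0.26 | 0.015-0.017 |
| 0.35 | 0.26-0.32 | 0.06-0.07 |
| 0.70 | 0.31-0.43 | 0.19-0.28 |

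Inflation appears in every row and is largest, relative to the fresh-data value, when the true effect is small. The sizes depend on the assumed geometry and smoothness; the direction does not.

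**Aim 2.** Choosing voxels by the arm difference raises the group-to-RSFC association, so that pre-condition becomes easier to meet. It does not directly raise the association between RSFC change and SDMT change within arms, which Step 2 also needs.

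**The case against.** The strongest reply is that the plan leaves a detail open and does not commit to an error. Much of that stands.

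- A reader might infer that a circular analysis is planned. No section says that values will come from surviving clusters. Specific Aims 1 and 2 use the same two named regions, which fits region values at least as well.
- A reader might infer that every way of completing the plan fails. A mask fixed in advance, from anatomy, an atlas or the pilot, avoids the circularity. It is simply not specified, and it would still need a correction across the two regions.
- A reader might take 7-10% as the trial's overall error. Specific Aim 1 tests RSFC only after SDMT, so with no effect on any outcome the overall error stays near .05. Section 5.3 also describes ordered testing; if the regions followed a stated order, the excess would disappear. No order between regions is given.
- A reader might infer that the next trial will be undersized. The documents give no RSFC effect size, say only that the pilot RSFC effects exceeded the SDMT value of 0.11, and list RSFC as one of four sources. They do not show that RSFC would set that sample size.
- Section 5.2.1 has all MRI processing and analysis done by someone blinded to condition. That is a real safeguard, but selecting voxels on a difference between coded groups produces the same bias.
- The SPSS statement is weak evidence on its own, since AFNI is named for the imaging correction.

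None of this supplies the missing definition, or makes a cluster threshold correct two region-level tests.

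**Conclusion.** The concern holds as a mismatch between the stated correction and the stated models, together with an outcome value that is never defined. The stated rule cannot deliver a corrected .05 for two region-level ANCOVAs: after SDMT has passed and with no order between regions, family-wise error is about 7-10%. If values were instead taken from surviving clusters, partial eta-squared would have a voxel-level floor of 0.101 to 0.159 with 66 analysed, under assumed voxel thresholds of .01 to .001, and the Aim 2 group-to-RSFC pre-condition would be easier to meet.

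It would go too far to say that Aim 2 is satisfied by construction, because the RSFC-to-SDMT path is not directly inflated. The SDMT test, which leads the hierarchy, is unaffected. The point should be settled before unblinding because a named primary outcome and all of Aim 2 rest on the definition.

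**What to change.** In section 5.3 and in Specific Aims 1 and 2:

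1. Define, before unblinding, one RSFC value per participant, visit and region, from a mask fixed independently of this trial's group result. One option is the mean Fisher-z correlation over an anatomical, atlas or pilot-based mask.
2. Use that same value for the ANCOVA, partial eta-squared, Cohen's d and the Aim 2 mediator.
3. Reconcile the two region lists, and control error across the named regions with Holm or with a stated fixed order that continues the step-down.
4. Keep the 3dClustSim map for localisation. Take no effect size or mediator value from its surviving clusters.

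The cost is wording; the structural scans are already planned. There are two statistical costs. A whole-region mean can dilute a focal effect. With Holm, the first step for two regions is at .05/2 = .025; assuming partial eta-squared 0.11 for RSFC, power falls from 0.80 to 0.71 at N = 66, and from 0.90 to 0.84 at N = 88. A fixed order keeps .05 for the first region, but the second is then tested only if the first succeeds.
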